Three ERPs will be measured: 1) the late positive potential (LPP), 2) the reward positivity (RewP), and 3) the P1. The LPP is a measure of sustained attention to affective stimuli generated by a network of brain areas involved in emotional processing and is larger for positive than neutral stimuli (Y. Liu, Huang, McGinnis-Deweese, Keil, & Ding, 2012; Schupp et al., 2000). It is blunted in depression (MacNamara, Kotov, & Hajcak, 2016; Weinberg, Perlman, Kotov, & Hajcak, 2016) but increases with behavioral therapies (Garland, Froeliger, & Howard, 2015; Leutgeb, Schäfer, & Schienle, 2009), suggesting that it indexes a state-related abnormality. The RewP is a measure of initial responsiveness to reward generated by the ventral striatum in response to feedback indicating desirable outcomes (Carlson, Foti, Mujica-Parodi, Harmon-Jones, & Hajcak, 2011; Foti, Weinberg, Bernat, & Proudfit, 2015; Holroyd, Krigolson, & Lee, 2011; Proudfit, 2014). It is blunted during episodes of depression (Foti, Carlson, Sauder, & Proudfit, 2014; W. Liu et al., 2014) and remission (Weinberg & Shankman, 2016; Whitton et al., 2016) and prior to first-onset depression (Bress, Foti, Kotov, Klein, & Hajcak, 2013; Nelson, Perlman, Klein, Kotov, & Hajcak, 2016), suggesting that it is a trait marker of reward system vulnerability. The P1 is an index of early visual attention generated in the extrastriate cortex (Di Russo, Martínez, Sereno, Pitzalis, & Hillyard, 2002). The P1 for affectively neutral stimuli is not influenced by depression (Dai & Feng, 2011; Dai, Wei, Shu, & Feng, 2016; Zhao et al., 2015). It is included to assess whether the effects of Engage are *specific* to reward systems. Behavioral activation will be assessed with the Behavioral Activation for Depression Scale (BADS) (Kanter, Mulick, Busch, Berlin, & Martell, 2007), and additional behavioral and self-report measures of reward processing are included for hypothesis generation.

Aims and Hypotheses

Primary aim: To study target engagement of the reward system in Engage.

H1: Engage-treated participants will have greater increase in LPP and BADS from baseline to week 9, but not in RewP and P1, compared to ST-treated participants.

H2: The course of LPP will be significantly associated with the course of BADS in Engage-treated participants.

Secondary aim: To identify predictors of change in anhedonia with Engage.

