SH1: Change in LPP for each assessment interval (baseline-3 weeks, 3-6 weeks) predicts severity of anhedonia at the next assessment time (6, 9 weeks) in Engage, but not in ST participants.

SH2: Change in BADS for each assessment interval predicts severity of anhedonia at the next assessment time in Engage, but not in ST participants.

Analysis Plan

We anticipate that approximately 15% of patients will fail to comply with the treatment protocol. Therefore, we will recruit 85 depressed older adults to meet our goal of 70 participants.

Descriptive Statistics

We will use graphical methods (e.g., box-plot) to examine the distribution and outliers of each clinical and demographic variable. If distribution assumptions are violated, we will use transformations or bootstrapping. In comparisons between Engage- and ST-treated subjects, we will include in regression models any variables (e.g. antidepressant use) that are unbalanced in these groups. We will control the overall Type I error rate at 5% after adjusting for multiple comparisons using Holm's stepdown procedure.

Analyses for Primary Hypotheses

H1. Engage-treated participants will have greater increase in LPP and BADS from baseline to week 9, but not in RewP and P1, compared to ST-treated participants. We will use separate mixed-effects regression models for the dependent variables (LPP and BADS assessed at baseline and weeks 3, 6 and 9). Our model will include fixed effects for age, time, sex, antidepressant use, and other variables when they differ between groups. Higher order(s) of the time variable (e.g., quadratic, cubic, etc.) or time as a categorical variable will be investigated. A significant interaction between time and treatment group will confirm our hypotheses. Separate mixed-effects models will be constructed with RewP and P1 assessments at baseline, weeks 3, 6 and 9 as dependent variables; we expect a weak time x group interaction, if any, for these variables because RewP remains blunted even in remitted depression and P1 is unrelated to reward function. While we do not expect to have power to test non-inferiority of RewP and P1 in Engage compared to ST, the proposed analysis will offer preliminary data on lack of change over time during treatment in RewP and P1 in both treatment arms.

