H2. The course of LPP will be significantly associated with the course of BADS in Engage-treated participants. We will construct a mixed model for LPP as a dependent variable, similar to H1, and include BADS at concurrent assessments as a predictor. A significant effect of BADS will confirm our hypothesis.

Analyses for Secondary Hypotheses

SH1. Change in LPP for each assessment interval (baseline-3 wks, 3-6 wks) predicts severity of anhedonia at the next assessment time (6, 9 wks) in Engage, but not in ST participants. SH2. Change in BADS for each assessment interval predicts severity of anhedonia at the next assessment time in Engage, but not in ST participants. In a linear mixed effects regression, change in LPP from baseline to week 3, week 3-6, and week 6-9 will be used to predict anhedonia severity (SHAPS-C) at 3, 6, and 9 weeks. We will include fixed effects for age, time, gender, and antidepressant use. We will repeat this analysis for BADS (SH2). A significant effect for LPP or BADS will confirm our hypotheses. We chose this correlative analysis rather than a mediation analysis because we are only powered to detect a very large mediation effect.

Missing Data

The proposed mixed-model analysis provides valid inferences when data are missing at random (Hedeker & Gibbons, 2006). To assess the sensitivity of the missing-at-random assumption, we will refit these models with pattern mixture models (Little, 1993), which entails fitting separate models for different drop-out patterns, and then assessing if intervention differences are sensitive to these patterns. To determine whether overall treatment effects, adjusting for study completer status, differ from the analogous control group's estimated differences, we will also employ the pattern-mixture methodology that provides for a way of taking weighted averages of these differences. In the event that we use generalized estimating equations due to untenable distributional assumptions in mixed effect models, we will use Robins's inverse probability weighted estimator (Robins, Rotnitzky, & Zhao, 1995).

Comment on Mixed-Model Analyses

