Mixed-effects models will include an age-group level random intercept to account for correlation among Engage- and ST- treated participants matched by age groups. In models where repeated measures are analyzed, we will include another subject-level random intercept nested within age-group to account for correlations among repeated measures and will include a random slope parameter.

Correction for Multiple Comparisons

We will control the study-wide false discovery rate for all hypotheses using the Benjamini-Hochberg method (Benjamini & Hochberg, 1995).

Power

H1. With 35 participants in each group, we will have 80% power at an alpha=2.5% to detect a difference of greater than or equal to 0.8 standard deviations in LPP and BADS change from baseline to 9 weeks, assuming a range of intra-class correlation coefficients for repeated measures ($\rho=0.2$ to 0.5) and an attrition rate of 10%. Our estimate of power is conservative as it is based on a pre-post test of mean difference between two treatment groups, whereas our analytic plan will use repeated measures to detect difference in slopes of LPP or BADS change over time. This study is not powered to detect non-inferiority of RewP and P1 in Engage vs. ST.

H2. With 35 participants in the Engage group, we will be able to estimate the correlation between LPP and BADS with a 95% confidence interval width of 0.15-0.47 for a range of correlations (0.6-0.9).

Patient Study Participants

Subject Population

There are two treatment arms to this study. Arm 1 patient participants will be 70 older adults (age ≥ 60) with MDD, 35 per treatment group. Diagnosis will be determined by the Structured Clinical Interview for DSM-5 (SCID) (First, Williams, Karg, & Spitzer, 2015). Participants will be free of major medical comorbidities and either free of antidepressants or on a stable dose for at least 12 weeks with a plan to continue on the same dose for the duration of the study.

Arm 2 patient participants will be older adults who report significant symptoms of depression but do not meet study criteria due to insufficient symptoms and/or severity, a recent change in medication, or past psychiatric comorbidity that does not contribute significantly to the current clinical presentation. These individuals will be "practice case" participants and will receive therapy from therapists undergoing training to administer therapy for the study.

Recruitment

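### Two multiplicity rules, Holm at 5% and study-wide Benjamini-Hochberg with no FDR level or test list, are left unreconciled; if the Holm promise covers the hypotheses, Benjamini-Hochberg does not deliver it

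*Combined protocol and SAP*

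**What the plan says.** Two statements deal with multiple testing.

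- The last sentence of Descriptive Statistics: "We will control the overall Type I error rate at 5% after adjusting for multiple comparisons using Holm's stepdown procedure". The sentence before it concerns covariate adjustment in treatment comparisons: "In comparisons between Engage- and ST-treated subjects, we will include in regression models any variables" that are unbalanced between the groups.
- The whole of Correction for Multiple Comparisons: "We will control the study-wide false discovery rate for all hypotheses using the Benjamini-Hochberg method". It gives no q and lists no tests.

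The decision rules name no threshold and neither procedure. For H1: "A significant interaction between time and treatment group will confirm our hypotheses". For H2: "A significant effect of BADS will confirm our hypothesis". SH1 and SH2 are worded in the same way. H1 itself reads: "Engage-treated participants will have greater increase in LPP and BADS from baseline to week 9, but not in RewP and P1", compared with supportive therapy. RewP and P1 also get models: "Separate mixed-effects models will be constructed with RewP and P1 assessments at baseline, weeks 3, 6 and 9 as dependent variables". The plan says it is not powered for non-inferiority on those two and calls that analysis preliminary.

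The Power section gives 80% power for LPP and BADS at alpha 2.5%, with 35 per group, a 0.8 SD difference in change and 10% attrition. It does not link the 2.5% to either procedure.

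**The concern.** Holm controls the chance of any false rejection in its family. BH controls the expected share of false rejections among those made, which is a weaker guarantee once some hypotheses in the family are truly non-null. A plan can use both, on separate sets of tests, but this one does not say which tests belong to which.

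If both statements reach H1, the plan promises a 5% error property and prescribes a procedure that does not secure it. Whichever way the Holm sentence is read, BH cannot be run as written, because its result depends on q and on the number of tests, and neither is stated. Rule, q and family for a primary hypothesis could then be settled after the p-values are known.

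**Working it through.** **1. The plan's own power figure.** Inputs from the Power section: 35 per group less 10% gives 31.5; difference 0.8 SD of the change score; alpha 0.025, taken as two-sided because the plan does not say. Noncentrality = 0.8 × √(31.5/2) = 3.175. The normal approximation gives Φ(3.175 − 2.241) = 0.825; the two-sample t-test (61 df) gives 0.807. The stated 80% reproduces.

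**2. What the 2.5% implies.** It equals 5%/2, the natural allowance for LPP and BADS. For two tests it is the first critical value of Holm and also of BH at q = 5%, so it does not choose between them. It does not fit a larger family: the first step is 0.05/5 = 0.01 for five tests and 0.05/7 = 0.0071 for seven. Single-test power (t) at 0.01 is 0.696.

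**3. Family size (not stated).** There are four labelled hypotheses, five tests if LPP and BADS are separate, and seven if RewP and P1 count. SH1 and SH2 each also have an Engage part and a supportive-therapy part.

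**4. Critical values for five tests, smallest p first (q = 5% assumed).**

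| Rule | 1 | 2 | 3 | 4 | 5 |
|---|---|---|---|---|---|
| Holm | 0.01 | 0.0125 | 0.0167 | 0.025 | 0.05 |
| BH | 0.01 | 0.02 | 0.03 | 0.04 | 0.05 |

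**5. False LPP or BADS claim, limiting case.** Both H1 nulls true, tests independent, the other three p-values near zero, each endpoint claimed separately.

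- BH rejects at least one if the smaller p is at most 0.04 or both are at most 0.05: 1 − 0.96² + 0.01² = 0.0785.
- Holm: 1 − 0.975² = 0.0494.
- For scale, BH at q = 10% (assumed; found nowhere in the plan): 1 − 0.92² + 0.02² = 0.154.

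**6. Same error by simulation.** At least 500,000 draws per scenario; the other three effects real at d = 0.8 and independent; LPP-BADS correlation 0 and 0.5; q = 5%.

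| Procedure | At least one false LPP or BADS claim |
|---|---|
| BH, five tests | 6.6-7.1% |
| Holm, five tests | 3.7-3.9% |
| Holm, LPP and BADS only | 4.7-4.9% |

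**7. How often the rule alone changes a decision (q = 5%, LPP and BADS real at d = 0.8).**

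- Five tests under either rule: an LPP or BADS decision differs in about 6-9% of trials, whether or not the other three effects are real.
- Two tests under either rule: 0.4-0.8%. Here the rules part only when both p-values lie above 0.025 and at or below 0.05. With 0.03 and 0.04, for example, BH rejects both and Holm neither.

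**The case against.** The strongest reply is that there is no conflict. The section devoted to multiplicity assigns BH to all hypotheses, H1 is one of them, and the Holm sentence closes a paragraph on distributions and group imbalance, before the hypothesis analyses begin. On that reading Holm governs descriptive comparisons only. This is tenable and cannot be excluded. Against it, the sentence speaks of an overall error rate without restriction and follows one about regression comparisons between the treatment groups. Even if the reply is accepted, the missing q and test list remain.

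It can also be said that the error scenario is selected, with both H1 nulls true and three other effects real. That is fair: the scenario shows that 5% is not guaranteed, not that 7% is expected. The excess also arises only if LPP and BADS are claimed separately. If both must be significant, the false-claim rate under BH at q = 5% is below 1% with both nulls true and at most 5% with one.

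Three stronger readings are tempting, and the documents do not support them.

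- A reader might infer that the plan is silent on which rule decides H1. Taken literally, BH does; the fault is a second promise that is neither scoped nor withdrawn.
- A reader might take the 0.03 and 0.04 example as general. With five tests BH rejects both only if other p-values are small too, for instance two of the other three at or below 0.04.
- A reader might quote the error near 15%. It rests on q = 10%, which the plan never states.

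**Conclusion.** The point stands as an inconsistency to be resolved, conditional on the scope of the Holm sentence. If that sentence covers the hypotheses, the 5% it promises is not secured by the BH rule stated later. Under the assumptions in the working, the excess is moderate: about 7% instead of 5% for separate claims, with a limit of 7.85%. If it covers descriptive comparisons only, the error rates do not conflict, but BH still lacks its level and its tests. The practical effect is small for a two-test family at q = 5% and material for the study-wide family that the plan describes. The values of q, the family size, the correlation and the independence of the other tests are assumptions, because the plan gives none of them. Whether H1 needs one endpoint or both is a side question, but it has to be answered before any of these figures applies.

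**What to change.** Before outcome data are analysed, name one rule for H1, with its level and tests, and state whether H1 needs both LPP and BADS.

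**Option A.** Apply Holm at an overall two-sided 5% to the LPP and BADS time-by-group interactions. Limit the 5% promise to that family and move the sentence out of Descriptive Statistics. Put H2, SH1 and SH2 under BH at a stated q, and report RewP and P1 descriptively. This fits the 2.5% power alpha; per-endpoint power is 0.85-0.88 when both effects are real. Cost: borderline H1 results that BH would pass cannot be claimed, and H2, which also serves the primary aim ("Primary aim: To study target engagement of the reward system in Engage"), has FDR control only.

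**Option B.** Keep BH for all hypotheses with a stated q and listed tests. Limit the Holm sentence to descriptive comparisons or delete it, drop the 5% overall claim for hypotheses, and restate the power alpha for that family. Cost: no familywise 5% claim, and per-endpoint power of about 0.76-0.79 at q = 5% if only LPP and BADS are real.

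If both endpoints are required, the 80% power statement also needs restating: joint power is 0.77-0.81 with each at 5%, or 0.65-0.72 with each at 2.5%.

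Either option changes SAP wording only; sample size and data collection stay as they are.

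### The multiplicity correction as written takes in RewP and P1, two tests expected to be null; this makes their predicted null easier to obtain and costs power for LPP and BADS

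*Combined protocol and SAP*

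**What the plan says.** Two sections set a multiplicity rule. Correction for Multiple Comparisons states: "We will control the study-wide false discovery rate for all hypotheses using the Benjamini-Hochberg method". Descriptive Statistics states: "We will control the overall Type I error rate at 5% after adjusting for multiple comparisons using Holm's stepdown procedure". The first gives no false discovery rate level, and neither lists the tests in the family.

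H1, a primary hypothesis, has a positive and a negative half: "greater increase in LPP and BADS from baseline to week 9, but not in RewP and P1, compared to ST-treated participants". The decision rule, "A significant interaction between time and treatment group will confirm our hypotheses", stands after the LPP and BADS models and before the RewP and P1 models. For RewP and P1 the plan says only "we expect a weak time x group interaction, if any, for these variables", and adds that "the proposed analysis will offer preliminary data on lack of change over time during treatment in RewP and P1 in both treatment arms". The Power section repeats the caveat: "This study is not powered to detect non-inferiority of RewP and P1 in Engage vs. ST". No margin or other criterion is given for the negative half of H1.

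The H1 power statement covers LPP and BADS only: 35 per group, alpha 2.5%, 0.8 SD of change, 10% attrition, 80% power.

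**The concern.** A multiplicity correction protects against false positives. For LPP and BADS, where the claim is a difference, that is the right protection. For RewP and P1 the prediction is that Engage does not produce a greater increase, so the error that matters more is a missed difference, and any correction makes that error more likely. A family containing all of H1 therefore tilts the RewP and P1 results toward the prediction. Two extra tests that are truly null also tighten the cut-offs that LPP and BADS must meet.

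The term non-inferiority also points the wrong way. It bounds how far Engage could fall short of supportive therapy (ST). Denying a greater increase needs the opposite bound: how much larger the Engage increase could still be.

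At stake are how a reader interprets a flat RewP or P1 result, and the power of the two tests the trial was sized for.

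**Working it through.** **Inputs from the plan.** 35 per group; 10% attrition, so 35 × 0.9 = 31.5 analysed per group; alpha 2.5%; 0.8 SD, taken in units of the SD of change; comparison of mean pre-post change between two groups (all from Power, H1).

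**Assumptions.** Level 5% for both procedures. Four families: LPP and BADS (2 tests); all of H1 (4); all of H1 plus H2, SH1 and SH2 (7); the last without RewP and P1 (5). H2, SH1 and SH2 are either null or each have noncentrality 2.8. Tests are independent unless stated.

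**Step 1: the stated power.** Noncentrality = d × √(n/2). With n = 31.5: 0.8 × √15.75 = 0.8 × 3.969 = 3.175. Two-sided t-test power at 2.5% is 0.807, and 0.800 with n = 31. The stated 80% is reproduced.

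**Step 2: the cut-offs.** Benjamini-Hochberg compares the k-th smallest of m p-values with 5% × k/m. To reject exactly LPP and BADS, the larger of their p-values must fall below:
- m = 2: 5% × 2/2 = 0.05
- m = 4: 5% × 2/4 = 0.025
- m = 7: 5% × 2/7 = 0.0143

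**Step 3: missed RewP difference.** Let RewP truly differ by 0.5 SD and LPP and BADS by 0.8 SD. Uncorrected at 5%, RewP noncentrality is 0.5 × 3.969 = 1.984 against a critical value of 2.00, so about half of trials miss it. Simulation (400,000 runs) gives:

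| Rule | RewP non-significant |
|---|---|
| Uncorrected 5% | 50% |
| Benjamini-Hochberg, 4 tests | 57% |
| Benjamini-Hochberg, 7 tests | 57% to 66% |
| Holm, 4 tests | 64% |
| Holm, 7 tests | 70% to 75% |

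If RewP truly does not differ, the non-significance rate moves only from 95.0% to 96.6% (4-test Benjamini-Hochberg).

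**Step 4: power for LPP and BADS.** True effects are 0.8 SD in both and none in RewP or P1:

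| Comparison | LPP power without RewP, P1 | LPP power with them |
|---|---|---|
| Benjamini-Hochberg, 2 vs 4 tests | 0.870 | 0.795 |
| Benjamini-Hochberg, 5 vs 7, H2/SH1/SH2 null | 0.769 | 0.725 |
| Benjamini-Hochberg, 5 vs 7, H2/SH1/SH2 at 2.8 | 0.857 | 0.818 |
| Holm, 2 vs 4 tests | 0.865 | 0.751 |

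Power to reject LPP and BADS together falls from 0.771 to 0.656 (Benjamini-Hochberg, 2 vs 4) and from 0.766 to 0.578 (Holm, 2 vs 4).

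If RewP truly changes by 0.8 SD, the Benjamini-Hochberg cost shrinks, because a rejected RewP relaxes the other cut-offs. From five to seven tests with H2, SH1 and SH2 null it vanishes (0.768 vs 0.770). From two to four tests some cost remains (0.865 vs 0.829, run with correlation 0.3).

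**Step 5: what an unadjusted interval shows.** The 95% half-width is 2.00 × √(2/31.5) = 2.00 × 0.252 = 0.50 SD of change. An observed difference of zero would still leave a greater Engage increase of about 0.5 SD possible.

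**The case against.** A reader might infer that the plan counts non-significant RewP and P1 results as confirming H1. The documents do not support that. The only confirmation rule is a significant interaction, placed with LPP and BADS; the RewP and P1 output is called preliminary, and lack of power is acknowledged twice. What stands is narrower: the negative half of H1 has no criterion at all.

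A reader might also infer that a missed RewP effect would be counted as evidence of specificity. The Overview gives that role to P1. RewP is itself a reward measure, described as a trait marker. Since the primary aim is engagement of the reward system, a significant RewP result could be presented as a positive finding, so protecting it against false positives is not senseless. The fix has to deal with this.

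Three further points limit the size:
- Most of the miss risk is low power. The 50% at 0.5 SD exists with no correction.
- A RewP p-value of 0.03 would often survive. With LPP and BADS rejected in a four-test family the cut-off is 5% × 3/4 = 0.0375; in a seven-test family with four other rejections it is 5% × 5/7 = 0.0357. With only LPP and BADS rejected in the seven-test family it is 5% × 3/7 = 0.0214, and 0.03 fails.
- The family is undefined. The planned alpha of 2.5% equals 5%/2, which fits a family of LPP and BADS alone. But that figure appears only in the power statement, while the operative rule covers all hypotheses.

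It is also inexact to say that Benjamini-Hochberg spends an error budget on the two tests. Its cut-offs depend on the other p-values, and Step 4 shows the cost can disappear.

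**Conclusion.** The concern holds in direction under either stated rule, with moderate size. As written, RewP and P1 fall in the corrected family. For a true 0.5 SD RewP difference, correction adds about 7 to 16 points to a 50% miss rate under Benjamini-Hochberg (57% to 66%) and 14 to 25 points under Holm (64% to 75%). When both are null, their inclusion costs LPP and BADS about 4 to 8 points of power each under Benjamini-Hochberg, and about 11 points under Holm from two to four tests (0.865 to 0.751).

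These figures rest on the assumed families, the 5% level, effects in SD of change and 31.5 per group. The two conflicting procedures alone change the size of both effects, so they must be reconciled in any case. The documents do not show that the plan intends to treat a non-significant control test as proof of no change; they leave the question open.

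**What to change.** 1. Choose one procedure and one level, and make Descriptive Statistics and Correction for Multiple Comparisons agree.
2. List the corrected family: the LPP and BADS interactions from H1, plus H2, SH1 and SH2. SH1 and SH2 also predict no effect in ST, so say that their entries are the tests of the positive prediction.
3. State that the RewP and P1 interactions of time with treatment are control analyses outside the family, reported at unadjusted two-sided 5% with the 95% confidence interval for the Engage-minus-ST difference in change. The upper limit shows how large a greater increase remains possible. Use this in place of the non-inferiority wording in the H1 analysis and Power sections.
4. State that a non-significant control result is not evidence of no change, and that no confirmatory positive claim will be made from these unadjusted tests.

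The cost is wording only; no visit, measure or sample size changes. The downside is a chance of up to about 10% that at least one control test is significant by luck (1 − 0.95² = 9.75% if the two are independent), which makes the predicted pattern slightly harder to obtain. The change does not cure the low power for RewP and P1, but the interval makes it visible.

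### H1's 80% power reproduces in SDs of the change score, where the stated ICC range has no effect; in outcome SDs it is 59–81%. Name the SD, and state a common baseline mean for Arm 1.

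*Combined protocol and SAP*

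**What the plan says.** The Power section, H1, gives 80% power with 35 participants per group, alpha 2.5% and 10% attrition. The effect is a "difference of greater than or equal to 0.8 standard deviations in LPP and BADS change from baseline to 9 weeks", and the calculation is made "assuming a range of intra-class correlation coefficients for repeated measures" running from 0.2 to 0.5. It adds: "Our estimate of power is conservative as it is based on a pre-post test of mean difference between two treatment groups", whereas the analysis will use all the repeated measures.

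Under Analyses for Primary Hypotheses, H1, baseline is one of the outcome time points. The model is described thus: "Our model will include fixed effects for age, time, sex, antidepressant use, and other variables when they differ between groups". The decision rule is: "A significant interaction between time and treatment group will confirm our hypotheses". The form of time is not settled: higher-order terms "or time as a categorical variable will be investigated". The Comment on Mixed-Model Analyses says the repeated-measures models "will include a random slope parameter" but gives no variance for it.

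Study Design says Arm 1 is randomised, and its table puts the baseline assessment before the first therapy session. Arm 2 is assigned according to training needs.

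**The concern.** The power sentence gives an effect in SDs of change and an ICC range side by side. In a comparison of mean change, the ICC matters only if the effect is expressed in SDs of the outcome, because it then converts outcome SDs into the SD of change. If the effect is already in SDs of change, there is nothing for it to do. So a reader cannot tell whether H1 has 80% power for 0.8 outcome SD or, at low ICC, for about 1.0. A null LPP or BADS result could be over-read as evidence against an effect that the trial was not sized to see.

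The plan offers the repeated-measures analysis as its margin of safety. How large that margin is depends on two things left open: the form of time, and whether Engage and supportive therapy are given separate means at baseline.

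**Working it through.** **Inputs.** From the Power section: 35 per group, 10% attrition (35 × 0.9 = 31.5 completers), alpha 0.025, effect 0.8 SD, ICC ρ = 0.2 to 0.5. Visits at baseline and weeks 3, 6 and 9 are coded 0, 1/3, 2/3, 1. Assumptions: two-sided testing, outcome variance 1 at baseline, compound symmetry, and random-slope variance T = 0 unless stated.

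Two-sided testing is inferred, not stated. The per-group size for 80% power at 0.8 SD is 31.0/0.9 = 34.4 two-sided and 25.5/0.9 = 28.4 one-sided, and the plan has 35.

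**1. The plan's figure.** In SDs of change the noncentrality is 0.8/√(2/31.5) = 3.175. With 61 df and critical t 2.298, power is 80.7%. This matches the stated 80%, and ρ does not appear.

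**2. The same test in outcome SDs.** The SD of change is √(2(1−ρ)), so the standardised effect is 0.8/√(2(1−ρ)) = 0.632/0.676/0.730/0.800 at ρ = 0.2/0.3/0.4/0.5. Power is 58.6/65.0/72.5/80.7%. One-sided 2.5% gives 70/75/81/88%, so it does not rescue the low end. Conversely, 0.8 SD of change equals 0.8 × √(2(1−ρ)) = 1.01/0.95/0.88/0.80 outcome SD.

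**3. The margin from repeated measures, with a group effect at baseline.** For a linear slope over the whole period, the sum of squares of the visit times about their mean is 5/9, so the per-subject variance is (1−ρ)/(5/9) = 1.8(1−ρ), against 2(1−ρ) for pre-post. With categorical time, the completers' week-9 contrast is the pre-post test and gains nothing.

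**4. Common baseline mean, week-9 contrast.** The variance is 1−ρ² in outcome units, or (1−ρ²)/(2(1−ρ)) = (1+ρ)/2 in squared SDs of change.

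| Power (%), T = 0, ρ = 0.2/0.3/0.4/0.5 | SDs of change | Outcome SDs |
|---|---|---|
| Pre-post | 80.7 throughout | 58.6/65.0/72.5/80.7 |
| Slope, baseline group effect | 85.0 throughout | 63.7/70.1/77.4/85.0 |
| Week-9 contrast, common baseline | 96.2/94.7/93.0/91.1 | 82.4/84.6/87.5/91.1 |

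Keeping dropouts' earlier visits moves the slope test with a baseline group effect up by only about 1 to 2 points.

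**5. Sensitivity to the random slope.** With slope variance T, the variance of change is 2(1−ρ)+T and the common-baseline variance is 1+T−ρ². At T = 0.4 (an assumption), the common-baseline week-9 contrast has 93.7/92.0/90.2/88.3% in SDs of change and 66–74% in outcome SDs. Pre-post in outcome SDs is then 48–65%.

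**6. The omnibus interaction.** If time is categorical, the time × group test has 3 df. With a common baseline and a linear effect in SDs of change, it has 95/92/88/84% power at T = 0 and 89/85/81/78% at T = 0.4. The week-9 figures therefore do not describe that test.

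**The case against.** The strongest reply is that nothing is miscalculated. The sentence attaches the SD to change, the plain reading is SDs of the change score, and there 80% holds at every ICC in the range. An input with no effect is redundant, not wrong. The plan also calls its figure conservative, and on that reading it is: the linear slope test gives about 85% even with a group effect at baseline. All of this stands. A reader might infer that H1 is underpowered at 59%, but that follows only if outcome SDs were meant, and the text does not say so.

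The common baseline may also already be intended. The list of fixed effects names no group main effect, which, taken literally with time zero at baseline, is a common-baseline model. But the list omits the time × group interaction too, so it may not be exhaustive. The point is unstated either way.

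Two further inferences are tempting and should not be drawn. One is that a common baseline secures 80% on any reading: in outcome SDs with slope variance 0.4 it gives only 66–74%. The other is that 2.5% is a floor because a step-down over LPP and BADS could release more alpha for the second test. The Descriptive Statistics section says "We will control the overall Type I error rate at 5% after adjusting for multiple comparisons" by Holm's procedure but does not limit it to those two outcomes, and Correction for Multiple Comparisons names Benjamini-Hochberg for all hypotheses. If Holm covered all four H1 outcomes, its first step would be 1.25% and pre-post power in SDs of change 72.4%.

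**Conclusion.** The point holds as an ambiguity and a missed efficiency, not as an arithmetic error. H1's 80% reproduces (80.7%) in SDs of the change score, with the ICC range idle. In outcome SDs the same test has 59–81% and reaches 80% only at ICC 0.5. The documents do not settle the SD or the sidedness.

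A stated common baseline mean lifts the week-9 contrast above pre-post by 10 to 15 points in SDs of change, and by 10 to 24 in outcome SDs. Measured against the slope test with a baseline group effect, the gain is smaller: 6 to 11 and 6 to 19 points. These gains assume 31.5 completers per group, two-sided 2.5% per outcome, compound symmetry and no random-slope variance. A slope variance above zero reduces them, and the plan gives none.

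**What to change.** 1. In the H1 models for LPP and BADS, state that the randomised Arm 1 groups share a common baseline mean, or adjust for the baseline value. Name one 1-df primary test in advance: either the week-9 group contrast, which matches H1's own time frame, or the linear time × group slope. Do not rely on the 3-df categorical interaction.

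2. Name a small-sample degrees-of-freedom method, such as Kenward-Roger. In simulation with uncorrected standard errors, the common-baseline slope test had type I error of 3.0–3.4% against 2.5%. The baseline-adjusted week-9 analysis held 2.3–2.6%. Performance with Kenward-Roger was not simulated.

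3. Restate the power sentence: 80% for 0.8 SD of the change score, two-sided 2.5% per outcome, equal (with no random-slope variance) to about 1.0 outcome SD at ICC 0.2 and 0.8 at ICC 0.5. Drop the ICC range, or give power at each ICC for the chosen model with its random-slope assumption. Do not describe 2.5% as a floor unless the multiplicity procedure and its family are first settled.

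The cost is SAP and power wording, with no extra data or participants. The common baseline rests on randomisation and on baseline being measured before session 1, so it applies to Arm 1 only.
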